4.1 Participants

Crohn's disease patients will be identified in the Gastroenterology clinics at Guy's and St Thomas' NHS Foundation Hospital.

4.2 Inclusion criteria

- 1. Age 18 to 50 years.
- 2. Confirmed diagnosis of Crohn's disease diagnosed according to standard clinical, endoscopic, radiological or histological criteria.
- 3. Mild to moderately active Crohn's inflammation as defined by one or more of a raised CRP >10mg/L, faecal calprotectin >150 and a CDAI >150 but <320.
- 4. Active Crohn's inflammation in at least one segment of ileum or colon on a colonoscopy or flexible sigmoidoscopy.
- 5. No immunomodulatory treatment (thiopurines, methotrexate, tacrolimus, anti-TNFalpha antibody therapy, anti-alpha4beta7 antibody therapy, anti-p40 antibody therapy) currently or within the last 3 months.
- 6. Able to comply with all study requirements.
- 7. For females only, willingness to practice continuous effective contraception (see below) during the study and a negative pregnancy test on the day(s) of screening and vaccination.
- 8. Agreement to refrain from blood donation during the course of the study.
- 9. Provide written informed consent.

4.3 Exclusion criteria

- 1. Participation in another research study involving receipt of an investigational product in the 30 days preceding enrolment, or planned use during the study period.
- 2. Prior receipt of an investigational vaccine likely to impact on interpretation of the trial data.
- 3. Prior receipt of an adenoviral vectored vaccine in the last 12 months.
- 4. Administration of immunoglobulins and/or any blood products within the three months preceding the planned administration of the vaccine candidate.
- 5. Any confirmed or suspected immunosuppressive or immunodeficient state, including HIV infection; asplenia; recurrent, severe infections.
- 6. Any immunosuppressive medication currently or within the preceding 3 months including corticosteroids (except inhaled steroid or topical steroid), thiopurines, methotrexate, tacrolimus and any biological therapy.
- 7. History of allergic disease or reactions likely to be exacerbated by any component of the vaccine (e.g. Egg allergy)
- 8. Any history of hereditary angioedema, acquired angioedema, or idiopathic angioedema.
- 9. Any history of anaphylaxis in relation to vaccination.
- 10. Unable to provide written informed consent.
- 11. Pregnancy, lactation or willingness/intention to become pregnant during the study.
- 12. History of cancer (except basal cell carcinoma of the skin and cervical carcinoma in situ).
- 13. History of serious psychiatric condition likely to affect participation in the study.
- 14. Bleeding disorder (e.g. Factor deficiency, coagulopathy or platelet disorder), or prior history of significant bleeding or bruising following IM injections or venipuncture.
- 15. Any other serious chronic illness requiring hospital specialist supervision.
- 16. Suspected or known current alcohol abuse as defined by an alcohol intake of greater than 42 units every week.
- 17. Suspected or known injecting drug abuse in the 5 years preceding enrolment.
- 18. Seropositive for hepatitis C (antibodies to HCV).
- 19. Seropositive for hepatitis B surface antigen (HBsAg).
- 20. Any clinically significant abnormal finding on screening biochemistry or hematology blood tests, urinalysis, or a positive swab test for SARS-COV-2 (Covid-19) at screening.
- 21. Any other significant disease, disorder or finding which may significantly increase the risk to the participant because of participation in the study, affect the ability of the participant to take part in the study or impair interpretation of the study data.

4.4 First participants

The first participant in Group 1 will be vaccinated alone and then reviewed 48 hours following vaccination. The chief investigator (CI) and the chair of the Safety Review Committee (SRC) will be asked to provide the decision on whether to proceed after the safety review of the first participant. If there are no safety concerns, another two Group 1 participants will be vaccinated at least one hour apart, and reviewed in a further 48 hours. The CI and the chair of the SRC will be asked to provide the decision on whether to proceed with the vaccination of a further 3 participants in Group 1 and 1 participant in Group 2 following safety review of the previous vaccinated participants. This review will include the results of safety blood tests at day 7 post vaccination.

The same procedure will apply for the first participant in Group 2. He/she will be vaccinated ahead of the other participants. The profile of adverse events from that participant will be examined and no other participants will be vaccinated until at least 48 hours have elapsed following this participant being vaccinated.

The first participant in group 3 will be vaccinated alone and then reviewed 48 hours following vaccination. The chief investigator (CI) and the chair of the Safety Review Committee will be asked to provide the decision on whether to proceed after the safety review of the first participant. If there are no safety concerns, another two Group 3 participants may be vaccinated at least one hour apart, and reviewed in a further 48 hours. The CI and the chair of the SRC will be asked to provide the decision on whether to proceed with vaccination at the next highest dose following safety review of the previous vaccinated participants. This review will include the results of safety blood tests at day 7 post vaccination.

The first participant in group 4 will be vaccinated alone and then reviewed 48 hours following vaccination. The chief investigator (CI) and the chair of the Safety Review Committee will be asked to provide the decision on whether to proceed after the safety review of the first participant. If there are no safety concerns, another two Group 4 participants may be vaccinated at least one hour apart, and reviewed in a further 48 hours. After 3 subjects in group 4 have been vaccinated and followed up for 7 days, an interim safety review will be performed.

The prime vaccination with ChAdOx2 HAV of group 5 participants will take place on day 0 and the boost vaccination of MVA HAV on day 56, for all participants.

4.5 Interim safety review

Interim safety reviews with the Chair of the Safety Review Committee are planned after the first participant in groups 1-4. Safety reviews with the SRC are planned prior to dose escalation of each vaccine administration. The Chair of the SRC will be consulted to provide a review of safety data and adverse events in the first participant of groups 1-4

before proceeding to the next participant in group 1-4. Interim safety data may also be made available to manufacturers (in coded format) as specified in the contract with the manufacturer(s). Safety reviews will include an assessment of the profile and severity of adverse events reported.

4.6 Sequence of Enrolment and Vaccination of Participants (groups 1 and 2)

The first participant in Group 1 will be vaccinated alone and then reviewed 48 hours following vaccination. The chief investigator (CI) and the chair of the Safety Review Committee will be asked to provide the decision on whether to proceed after the safety review of the first participant. If there are no safety concerns, another two Group 1 participants will be vaccinated at least one hour apart, and reviewed in a further 48 hours. The CI and the chair of the SRC will be asked to provide the decision on whether to proceed with the vaccination of a further 3 participants in Group 1 and 1 participant in Group 2 following safety review of the previous vaccinated participants. This review will include the results of safety blood tests at day 7 post vaccination.

The same procedure will apply for the first participant in Group 2. He/she will be vaccinated ahead of the other participants. The profile of adverse events from that participant will be examined and no other participants will be vaccinated until at least 48 hours have elapsed following this participant being vaccinated.

Therefore, the possible numbers of participants to be vaccinated, assuming the adverse event profile allows progression to the high dose is 6 in each group. All participants will be issued with the telephone number of the investigator and encouraged to contact the investigators if there are any problems.

4.7 Sequence of Enrolment and Vaccination of Participants (groups 3-5)

The first participant in group 3 will receive 5×10^7 pfu of MVA HAV. This participant will be vaccinated ahead of any other participants and the profile of adverse events will be examined. No other participants will be vaccinated until at least 48 hours has elapsed following the first participant being vaccinated. The CI and the chair of the Safety Review Committee will be asked to provide the decision on whether to proceed after the safety review of the first participant. Provided no serious adverse reactions have occurred then a further two participants will be participant. The CI and the chair of the SRC will be asked to provide the decision on whether to proceed with vaccination at the next highest dose following safety review of the previous vaccinated participants. This review will include the results of safety blood tests at day 7 post vaccination.

The first volunteer in group 4 (2×10^8 pfu of MVA HAV) will be vaccinated alone and then reviewed 48 hours following vaccination. The Chief Investigator (CI) and the Chairperson of the Safety Review Committee (SRC) will be asked to provide the decision on whether to proceed after the safety review of the first volunteer. If there are no safety concerns, another two Group 4 participants may be vaccinated at least one hour apart, and reviewed in a further 48 hours. After 3 subjects in group 4 have been vaccinated and followed up for 7 days, an interim safety review will be performed.

The CI and the Safety Review Committee will be asked to provide the decision on whether to proceed with vaccinations in group 5 where 10 participants will be vaccinated with 5 x 10^{10} vp ChAdOx2 HAV followed by 2 x 10^8 pfu MVA HAV (8 weeks apart).

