3.3.1 Secondary outcome measures

Immunogenicity

Measures of immunogenicity may include:

ELISPOT to enumerate IFN-γ producing T cells

Other exploratory immunology may be carried out in collaboration with other specialist laboratories. This would involve transfer of serum/plasma and/or peripheral blood mononuclear cells (PBMC), but samples would be anonymised. Participants will be consented for this.

Sampling of exploratory immunology responses

20ml of whole blood will be taken at baseline (D0) and days 28 and 56 (groups 1 and 2). For Group 5 10ml of whole blood will be taken at screening, with 30ml taken at baseline (D0) and days 56 and 112 and an additional 20ml on days 28 and 84 of the study for use in assays to measure immune responses of various types to the vaccine.

Assessment of clinical response

All participants will undergo an evaluation of Crohn's disease activity at screening and at day 56 for groups 1-4. Group 5 will undergo an evaluation of Crohn's disease activity at screening, on day 56 and again on day 112. For Group 5, endoscopic scoring by flexible sigmoidoscopy or colonoscopy will be undertaken by the CD-SES (simple endoscopic score) at screening and at day 112.

Exploratory immunology may be carried out in collaboration with other specialist laboratories. This would involve transfer of serum/plasma and/or peripheral blood mononuclear cells (PBMC), but samples would be anonymised. Participants will be consented for this.

4 Trial design

This is a phase Ib open-label dose escalation study to assess the safety, tolerability and immunogenicity of the candidate Mycobacterium avium subspecies

paratuberculosis (MAP) vaccine, ChAdOx2 HAV in patients with active Crohn's disease aged 18-50.

Participants will be enrolled and doses will be escalated according to a study plan which will run as outlined in section 8.4.2.2 of the protocol and summarized in the table below:

Table 1 Summary of dosing regimen

Group	Dose
1 (n=6)	ChAdOx2 HAV, 2.5x1010 vp
2 (n=6)	ChAdOx2 HAV, 5x1010 vp
3 (n=3)	MVA HAV, 5x107 pfu
4 (n=3)	MVA HAV, 2x10 ₈ pfu
5 (n=10)	Prime boost Regime (doses depended on
	the results from Groups 1-4)

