6.1 Analysis of primary endpoint

Determining the Maximum Tolerated Dose (MTD) for ChAdOx2 HAV will depend on the response of patients in Group 1 and 2. As stated in the Group Holding rules, if 2 or more participants in Group 2 experience Grade 3 SAR lasting more than 48 hours, then the previously tolerated dose will be recorded as the MTD. If 2 or more participants in Group 1 experience Grade 3 SAR lasting more than 48 hours, then the trial will be put on hold pending an internal safety review.

If less than 2 participants in Group 2 experience the outcome stated above, then participants in Group 3 and 4 will be subject to the same criteria for the two doses of MVA HAV. If 2 or more participants in Group 4 experience Grade 3 SAR lasting more than 48 hours, then the previously tolerated dose will be recorded as the MTD. If 2 or more participants in Group 3 experience Grade 3 SAR lasting more than 48 hours, then the trial will be put on hold pending an internal safety review.

Once the MTDs for ChAdOx2 HAV and MVA HAV is determined, then participants in Group 5 will be subject to these doses. If 2 or more participants in Group 5 experience Grade 3 SAR lasting more than 48 hours, then the trial will be put on hold pending an internal safety review.

The proportion of all individuals per group who experience Grade 3 SAR lasting more than 48 hours at the end of follow-up will be estimated with a 95% exact confidence interval. The number with expected and unexpected AEs and all SAEs will be presented alongside, according to the sample table below:

Table 6 Summary of adverse events by Group

Number experiencin experiencin g Grade 3 enrolled SAR lasting more than 48 hours Proportion experiencin g Grade 3 SAR lasting more than 48 hours (95% CI)	Number of expected local reactogenicit y signs and symptoms for 7 days following the	Number of expected systemic reactogenicit y signs and symptoms for 7 days following the	Number of unexpected adverse events for 28 days following the vaccination	Number of serious adverse events during the whole study duration
---	--	---	---	--

		vaccination	vaccination	
Group 1				
Group 5				

The median and range of values of safety laboratory measures will be plotted by group at baseline (vaccination visit) and 7 days post vaccination.

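### Section 4.7 fixes the Group 5 doses while Table 1 and section 6.1 make them depend on earlier groups, and 6.1 has no route to an MVA HAV MTD if Group 2 meets the toxicity rule

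*SAP*

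**What the plan says.** Four places in the SAP bear on the Group 5 doses.

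- **Section 4.7.** The chief investigator and the Safety Review Committee decide whether "to proceed with vaccinations in group 5 where 10 participants will be vaccinated with 5 x 10^{10} vp ChAdOx2 HAV". The same sentence goes on to fix the boost at the higher of the two MVA HAV doses. Both are therefore the upper levels of their vaccines. The decision described is whether to go ahead; the doses themselves carry no condition.
- **Section 4, Table 1.** The Group 5 row reads "Prime boost Regime (doses depended on" and goes on to name Groups 1-4 as the source.
- **Section 6.1.** "Once the MTDs for ChAdOx2 HAV and MVA HAV is determined, then participants in Group 5 will be subject to these doses". The ChAdOx2 HAV rule is that "if 2 or more participants in Group 2 experience Grade 3 SAR lasting more than 48 hours, then the previously tolerated dose will be recorded", and that dose then counts as the MTD. The rule for the other vaccine has the same form: "If 2 or more participants in Group 4 experience Grade 3 SAR lasting more than 48 hours, then the previously tolerated dose will be recorded". The MVA HAV step opens with a condition: "If less than 2 participants in Group 2 experience the outcome stated above, then participants in Group 3 and 4 will be subject to". What follows there carries the ChAdOx2 HAV criteria over to MVA HAV.
- **Section 3.2.3.** If 2 or more participants in Groups 1-2 have the event at a given ChAdOx2 HAV dose, vaccination at that dose and above stops, and the dose below becomes the MTD. This MTD sentence names Groups 1-2 only. The holding rules that follow cover Groups 1-5 but do not mention an MTD.

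**The concern.** There are two linked problems.

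First, 4.7 gives Group 5 one dose pair regardless of results, while Table 1 and 6.1 let the results decide. The difference appears only when an upper dose has met the toxicity rule, which is the situation that a dose-escalation plan must settle in advance.

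Second, section 3.2.2 refers to 3.2.3 for the definition of the MTD, but the MTD sentence there covers ChAdOx2 HAV only. That leaves 6.1 as the sole definition of an MVA HAV MTD, and 6.1 reaches it through a condition on Group 2, which received a different vector. If Group 2 meets the rule, 6.1 records a ChAdOx2 HAV MTD and says nothing about how the MVA HAV MTD is obtained. It still requires both MTDs before Group 5. Section 4.7 starts Groups 3 and 4 without any Group 2 condition, so the two sections also differ on this.

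At stake are the MTD, which is the first-listed primary outcome measure in 3.2.2, and the doses for 10 of at most 28 participants.

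**Working it through.** **Plan's own figure.** The Table 1 group sizes sum to 6 + 6 + 3 + 3 + 10 = 28, which matches the maximum sample size in the synopsis. The SAP contains no power calculation or assumed event rate to reproduce.

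**The sections side by side, by outcome of Groups 2 and 4.** An event is a Grade 3 reaction lasting more than 48 hours, and the rule is met at 2 or more.

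| Outcome | Section 4.7 | Section 6.1 | Agree? |
|---|---|---|---|
| Neither group meets the rule | upper dose of each vaccine | the MTDs, taken here as the upper doses because no lower dose is recorded | yes |
| Group 4 only | upper dose of each vaccine | MVA HAV MTD is the previously tolerated dose | no, on the boost |
| Group 2 (with or without Group 4) | upper dose of each vaccine | ChAdOx2 HAV MTD is the previously tolerated dose; MVA HAV MTD not defined | no, on the prime; boost undefined in 6.1 |

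In the last row, 4.7 also conflicts with the bar in 3.2.3 on further vaccination at that ChAdOx2 HAV dose.

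**How often the sections would diverge.** Inputs: Group 2 has n = 6 and Group 4 has n = 3 (Table 1), with a threshold of 2 (section 6.1). The true event rate p is an assumption. It is taken as equal at both upper doses, with the groups independent and fully vaccinated.

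- Group 2 meets the rule: a = 1 − (1−p)^6 − 6p(1−p)^5
- Group 4 meets the rule: b = 3p²(1−p) + p³
- Either meets it: 1 − (1−a)(1−b)

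At p = 0.10:

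- a = 1 − 0.5314 − 0.3543 = 0.1143
- b = 0.027 + 0.001 = 0.028
- either = 1 − 0.8857 × 0.972 = 0.1391

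| Assumed p | Group 2 meets rule (6.1 has no MVA HAV branch) | Group 4 meets rule, if evaluated | Either (sections diverge) |
|---|---|---|---|
| 0.02 | 0.6% | 0.1% | 0.7% |
| 0.05 | 3.3% | 0.7% | 4.0% |
| 0.10 | 11.4% | 2.8% | 13.9% |
| 0.20 | 34.5% | 10.4% | 41.3% |
| 0.30 | 58.0% | 21.6% | 67.1% |

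Most of the divergence comes from Group 2, the same outcome for which 6.1 has no MVA HAV branch.

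**The case against.** The strongest reply is that 4.7 is a narrative of the expected path. Each step in it follows a decision to proceed, and the companion section 4.6 says outright that its numbers assume an adverse event profile that permits the high dose. On that reading 4.7 lacks only a qualifying phrase. This is plausible, and it is true that the sections agree when both upper doses are tolerated. But 4.7 does not carry the qualifier, and neither it nor Table 7 says how the Group 5 doses are set otherwise.

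A reader might infer that the plan would send 10 patients to a dose already found poorly tolerated. The SAP does not support that. Section 3.2.3 stops further vaccination at a ChAdOx2 HAV dose that meets the rule. The holding rules cover Groups 1-5, and a restart needs an internal safety review and a substantial amendment. Table 7 places a review before the first Group 5 vaccination. One gap remains: most of the holding rules require the same Grade 3 event twice, so two different Grade 3 reactions in Group 4 could meet the 6.1 criterion without necessarily triggering a hold.

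A reader might also infer that the MVA-alone part of the primary objective is lost if Group 2 meets the rule. It is not. The primary objective is safety and tolerability, and 6.1 and Table 6 report each group's proportion with an exact interval, and its adverse events, whatever happened in Group 2. What is left undefined is the MVA HAV MTD.

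Finally, the 6.1 condition may describe sequence only, since it never says that Groups 3 and 4 would be skipped. That is fair. The defect is a missing branch, not a stated exclusion.

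**Conclusion.** The point stands as an internal inconsistency with a missing branch. Section 4.7 disagrees with Table 1 and 6.1 on the Group 5 doses whenever Group 2 or Group 4 meets the toxicity rule. When Group 2 does, 4.7 also disagrees with 3.2.3, and 6.1 leaves the MVA HAV MTD undefined.

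It would go too far to say that Group 5 has no consistent dose under any outcome, because the sections agree if both upper doses are tolerated.

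The chance of divergence runs from about 0.7% at an assumed rate of 0.02 to 67.1% at 0.30. It rests on a single rate for two different vectors and on independence between groups, neither of which comes from the SAP. At low rates the conflict would seldom arise. The finding depends on the text and not on these percentages.

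The existing safeguards limit the safety consequence, so this is something that should be fixed, not a critical fault.

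**What to change.** Reconcile sections 3.2.3, 4.7 and 6.1 and Table 1 on two matters:

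1. One rule should state how the Group 5 doses follow from the results of Groups 1-4, and 4.7, Table 1 and 6.1 should all refer to it. If 4.7 is meant to describe only the path in which both upper doses are tolerated, it should say so.
2. Sections 6.1 and 4.7 should agree on whether and how the MVA HAV MTD is assessed if Group 2 meets the rule, and on what then follows for Group 5.

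Which dose and which rule apply is for the sponsor and the safety committee to decide. The SAP points to protocol section 8.4.2.2 for the escalation plan. That text is not available here, so the reconciled wording should be checked against it. The cost is a change of wording, with no added patients or visits.

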4.8 Assessment of severity

The severity of clinical and laboratory adverse events will be assessed according to the scales in Table 2-4.

Table 2 Severity grading criteria for local adverse events for intramuscular injections.

Adverse Event	Grade	Intensity
Erythema at injection site*	1	>3 -≤50 mm
	2	>50 -≤100 mm
	3	>100 mm
Swelling at injection site	1	>3 -≤20 mm
	2	>20 -≤50 mm
	3	>50 mm
Ulceration/necrosis of skin at injection site	1	-
	2	-
	3	Any

^{*}erythema or swelling ≤3mm is an expected consequence of skin puncture and will therefore not be considered an adverse event.

Table 3 Severity grading criteria for physical observations

	Grade 1	Grade 2	Grade 3	
	(mild)	(moderate)	(severe)	
Fever (oral)	37.6°C -38.0°C	38.1°C –39.0°C	>39.0°C	
Tachycardia (bpm)*	101 - 115	116 – 130	>130	
Bradycardia (bpm)**	50 – 54	40 – 49	<40	

Systolic hypertension (mmHg)	141 - 159	160 – 179	≥180
Systolic hypotension (mmHg)***	85 - 89	80 – 84	<80
Diastolic hypertension (mmHg)	91 - 99	100 – 109	≥110

^{*}Taken after ≥10 minutes at rest

Table 4 Severity grading criteria for local and systemic AEs.

GRADE 0	None: Symptom not experienced
GRADE 1	Mild: Short-lived or mild symptoms; medication may be required. No limitation to usual activity
GRADE 2	Moderate: Mild to moderate limitation in usual activity. Medication may be required.
GRADE 3	Severe: Considerable limitation in activity. Medication or medical attention required.

